4.7 Compliance

In accordance with regulatory requirements, the Investigator or designated site staff must document the amount of study medication dispensed and/or administered to study subjects, the amount returned by study subjects, and the amount received from and returned to the Sponsor (or representative), when applicable.

4.8 Evaluation of Efficacy

4.8.1 Hot Flash Diaries

Subjects will complete two different diaries during the study to record the incidence and severity of hot flashes and NTAs. A twice daily diary will be completed throughout the study and a Continuous Diary will be completed on days subjects are resident in the clinical pharmacology unit.

4.8.1.1 Twice Daily Diaries

Subjects will document the number of individual hot flashes experienced and rate the severity of each on a scale of mild, moderate or severe (1, 2, or 3). The diaries will be completed twice daily (evening and morning). The diaries will be completed for the 2 weeks prior to the baseline visit to ascertain eligibility, and from screening until the morning of Day 15 (the last entry will be the information from overnight). Subjects will also record the number of NTAs.

4.8.1.2 Continuous Diaries

While in the clinic on Days -1, 1 through 7, and Day 14, subjects will record in the hot flash continuous diary each hot flash and its severity (3 point scale of mild, moderate, or severe), as they occur during the day and night. Subjects will also be required to push a button on the skin conductance monitor when they sense a hot flash, and then record the event in the continuous diary. For Days -1 and 14, subjects will be provided with the continuous diary at the previous visit and instructed to start completing it upon waking in the morning on Days -1 and 14.

4.8.2 Sternal Skin Conductance Monitors

Studies have shown that rather than over-reporting hot flashes when they do not occur, women tend to under report them when asked to complete hot flash diaries, thus leading to inaccuracy. Objective assessment is therefore useful and can be achieved using a sternal skin conductance monitor. Sternal skin conductance monitors will be fitted on Day -1 (24 hours \pm 1 hour prior to

the planned study drug administration on Day 1) and will remain in place until after the Day 7, 24 hour assessments are completed (Day 8).

The sternal skin conductance monitors will be refitted around 30 minutes prior to study drug administration on Day 14 and remain in place until after the 24 hour assessments are completed on Day 15.

When fitted with the monitor, subjects will be required to push a button on the skin conductance monitor when they sense a hot flash, and then provide details of the hot flash in the continuous hot flash diary.

4.8.3 Luteinizing Hormone Analysis

Blood samples for analysis of LH will be collected every 60 minutes from time 0 (predose) to 8 hours on Days 1 and 7. The same sampling schedule will also be followed on Day -1, starting at a similar time to that planned for Days 1 and 7.

Luteinizing hormone samples will be collected as close to the nominal time point as possible. The allowable window for LH sample collection relative to dosing will be ± 5 minutes.

4.9 Pharmacokinetic Sampling Schedule

Blood samples for PK analysis will be collected at the following time points on Days 1, 7, and 14: predose, and 0.5, 1.0, 1.5, 2.0, 2.5, 3.0, 4.0, 5.0, 6.0, 8.0, 12.0, and 24.0 hours postdose. For Cohorts 3 onwards, additional samples will be collected at 48.0 and 72.0 hours after the Day 14 dose.

The predose sample will be collected within 30 minutes prior to dose administration.

Pharmacokinetic samples will be collected as close to the nominal time point as possible. Allowable windows for PK sample collection relative to dosing will be as follows: ± 2 minutes through 2 hours postdose, ± 5 minutes through 8 hours postdose, ± 10 minutes through 24 hours postdose and ± 30 minutes for the 48 and 72 hour postdose samples.

4.10 Evaluation of Treatment Safety

4.10.1 Adverse Events

All AEs will be recorded from the time the informed consent is signed until study exit, and SAEs occurring up to 30 days after the last dose of study medication should be reported.

4.10.1.1 Definitions

An AE is any untoward medical occurrence in a subject or clinical trial subject administered a medicinal product, which does not necessarily have a causal relationship with this treatment. An AE can therefore be any unfavorable and unintended sign (including an abnormal laboratory

finding, for example), symptom, or disease temporally associated with the use of a medicinal product, whether or not considered related to the medicinal product.

All events considered being untoward and unintended responses to a medicinal product related to any dose should be considered adverse drug reactions. The definition covers also medication errors and uses outside what is foreseen in the protocol, including misuse and abuse of the product. The phrase “responses to a medicinal product” means that a causal relationship between a medicinal product and an AE is at least a reasonable possibility (i.e., the relationship cannot be ruled out).

An SAE is and AE that at any dose:

- Results in death
- Is life-threatening (i.e., the subject was at risk of death at the time of the event; it does not refer to an event which hypothetically might have caused death if it was more severe)
- Requires inpatient hospitalization or prolongation of existing hospitalization (hospitalizations are defined as initial or prolonged admissions that include an overnight stay; hospitalization or prolonged hospitalization for technical, practical, or social reasons, in the absence of an AE, is not an SAE.)
- Results in persistent or significant disability/incapacity
- Is a congenital anomaly/birth defect
- Is considered to be an important medical event (based on medical and scientific judgment, important medical events that may not be immediately life-threatening, or result in death or hospitalization, but may jeopardize the subject or may require intervention to prevent one of the other outcomes listed)

An additional blood sample for the determination of NT-814 plasma levels should be taken in case of SAEs with reasonable possibility of relatedness to the study drug. The analysis of such PK samples will be conducted as soon as possible after the occurrence of the SAE.

Pregnancy itself is not considered an AE. However, any pregnancy complication, spontaneous or elective abortion (for medical reasons), still birth, neonatal death, or congenital anomaly will be recorded as an AE or SAE.

An unexpected adverse drug reaction is any adverse reaction, the nature or severity of which is not consistent with applicable product information (eg, Investigator’s Brochure for an unapproved IMP). Reports that add significant information on the specificity, increase of occurrence, or severity of a known, already documented serious adverse reaction constitute unexpected events.

A suspected unexpected serious adverse reaction is an SAE suspected to be related to the administered medicinal product; the nature or severity of the event is not consistent with applicable product information.

4.10.1.2 Severity and Relatedness Assessment

Severity will be classified as follows:

- Mild: Awareness of sign or symptom, but easily tolerated
- Moderate: Sign or symptom causes discomfort, but does not interfere with normal activities
- Severe: Sign or symptom of sufficient intensity to interfere with normal activities

The likely relationship of each AE to the medicinal product will be assessed according to the definitions below:

- Unrelated
- Possibly
- Probably
- Definitely

4.10.2 Clinical Laboratory Assessments

Clinical chemistry/ biochemistry and hematology sampling will be performed at screening and on Days -1, 8, 14, and early termination. The following clinical chemistry/ biochemistry parameters will be assessed: sodium, potassium, glucose, urea, creatinine, creatine kinase, albumin, calcium, phosphate, bilirubin (total), alkaline phosphatase, aspartate aminotransferase, alanine aminotransferase, gamma-glutamyl transferase, bicarbonate, magnesium, chloride, total protein, total cholesterol, low-density lipoprotein, high-density lipoprotein, triglycerides. The following hematology parameters will be assessed: red blood cells, white blood cells, hematocrit, hemoglobin, mean corpuscular volume, platelets, white blood cell differentials, prothrombin time, and activated partial thromboplastin time.

Urinalysis sampling will be performed on Days -1, 8, and 14. Urinalysis will include glucose, bilirubin, ketones, specific gravity, blood, pH, protein, urobilinogen, nitrites, leucocytes, and sedimentation.

Blood samples will be collected to assess estradiol, testosterone, FSH, ACTH, cortisol, TSH, T3, and T4 when the subjects are admitted to the unit on Day -1 and again prior to discharge on Day 15.

4.10.3 Vital Signs

Vital signs will include sitting and standing BP, HR, arterial oxygen saturation, oral body temperature, respiration rate, and weight. Vital sign assessments will be performed on Day -1 at a similar time to the same assessments that are planned predose on Day 1. The assessments will then be performed postdose for all other days in clinic and at a similar time on Day 15.

4.10.4 Twenty-four-hour Holter Monitoring

Subjects will be fitted with Holter monitors upon admission to the CPU on Day -1. These will remain in place until after the Day 7, 24-hour assessments are completed (on Day 8). Subjects will be fitted with Holter monitors again upon admission to the CPU on Day 14. These will remain in place until after the Day 14, 24-hour assessments are completed (on Day 15).

4.10.5 Electrocardiograms

On Days 1 and 14, resting 12-lead ECG data will be collected at the following timepoints: predose and at 0.5, 1.0, 1.5, 2.0, 2.5, 3.0, 4.0, 8.0, 12.0 and 24.0 hours (all +/- 15 mins).

The same assessment schedule is also required on Day -1, starting at a time similar to that planned for Days 1 and 14. The Day -1 and Day 1, 24 hour ECGs must be performed prior to the dose of study medication the following morning (on Days 1 and 2, respectively).

Once-daily ECG recordings will be just prior to dosing (approx. 30 mins) on all other days during the inpatient stay (Days 3 to 8).

4.10.6 Physical Examinations

A full physical examination will be performed at screening and Days 1, 8, and 15, and is composed of a review of the following body systems:

- General appearance
- Skin
- Head, eyes, ears, nose and throat
- Respiratory
- Cardiovascular
- Abdomen (including liver and kidneys)
- Musculoskeletal
- Neurological

Any abnormalities that are identified at screening will be documented on the medical history eCRF page. Any changes (including new and worsening findings) between screening and the final study visit should be captured as AEs on the AE eCRF page.

If an improvement/resolution of a physical examination finding documented in the subject's medical history occurs during the study, it should be recorded in the source document. If there is resolution of a physical examination finding previously noted as an AE, then the event resolution and stop date should be recorded on the AE eCRF page and documented in the subject's notes.

4.10.7 Medical History and Concomitant Diseases

The investigator must record all medically and clinical relevant information regardless of the time since the date of diagnosis. The history should include (but is not limited to):

- All current and past medications taken during 3 months before screening
- Relevant history of respiratory, cardiovascular, renal, gastrointestinal, hepatic, endocrine, hematological, neurological, psychiatric, and any other diseases

4.11 Protocol Deviation Reporting

Procedural deviations found by the clinical research associate during monitoring visits and data deviations captured on the eCRF and found through programming and examining the database will be collected. Examples of deviations are documented in the Protocol Deviation Criteria Form.

5 CHANGES IN THE CONDUCT OF THE STUDY OR PLANNED ANALYSIS

The conduct of the study and planned analyses are consistent with the study protocol (Version 4.0, dated 13 December 2016). The exposure response analysis on QTcB will not perform since this correction method is not regarded as appropriate ; per the Q&A E14, question 1.5 (available at http://www.ich.org/fileadmin/Public_Web_Site/ICH_Products/Guidelines/Efficacy/E14/E14_Q_As_R3_Step4.pdf).

6 QUALITY CONTROL AND QUALITY ASSURANCE METHODS FOR DATA ANALYSIS

Clinical source data will be entered into eCRFs, which will then be monitored by an independent Monitor designated by the Sponsor. All eCRF data will be processed according to the ICON Study Specific Procedure SSP DM-RELENT-1.01 Data Management Plan (DMP). The DMP describes eCRF data processing, edit checks, data query management, medical dictionary coding, SAE reconciliation, data transfers, and data quality review through database lock or any necessary reopening of the database. After database lock, the data will be retrieved from the database and analysed using SAS[®] 9.3 or higher.

7 PHARMACOKINETIC ASSESSMENTS

7.1 Pharmacokinetic Assessments

The bioanalyses for plasma NT-814 concentrations will be performed by Aptuit Medicines Research Centre and the PK analyses will be done by Parexel and described in a separate document.

8 STATISTICAL METHODS

8.1 General

The statistical analysis will be conducted following the principles specified in the International Council for Harmonization, formerly the International Conference on Harmonization, Topic E9 Statistical Principles for Clinical Trials (CPMP/ICH/363/96).

All statistical tabulations and analyses will be done using SAS[®], Version 9.3 or higher.

Unless otherwise noted, continuous variables will be summarized using number of non-missing observations, arithmetic mean, standard deviation (SD), median, minimum, and maximum; categorical variables will be summarized using the frequency count and the percentage of subjects in each category.

In the data listings, study day relative to first dose of study drug may be presented. Study day relative to first dose will be calculated as: event date – first dose date (+ 1 if event date \geq first dose date). That is, there is no Day 0.

Baseline will be the latest available measurement prior to the first study drug administration in the study, unless otherwise specified.

For safety summaries, the unscheduled and repeat assessments will not be summarized; however, all results will be included in the data listing.

All subject level data, including those derived, will be presented in the individual subject data listings.

Unless otherwise noted, the analyses will be done by treatment (50 mg NT-814, 100 mg NT-814, 150 mg NT-814, etc... (XX mg NT-814), Total NT-814 (if applicable), placebo). Data for the placebo subjects will be combined across cohorts prior to any summaries.

8.2 Handling of Dropouts or Missing Data

For the calculation of the luteinizing hormone AUC_{0-8} at any visit,

- If more than one time point is missing, then the AUC won't be calculated and will be considered as missing.
- If one of the following time points is missing (T1, T2, T3, T4, T5, T6, T7) then the AUC will be calculated without the missing time point.
- If one of the following time points is missing (T0 or T8), then the AUC won't be calculated and will be considered as missing.

For the derivation of the daily scores in the efficacy section, the daily derivation will not be calculated and will be treated as missing if the results of the corresponding day are incomplete:

Twice daily diary

- The hot flash data are collected twice (day time and night time) and if either period is not complete, then the whole day will be considered incomplete and therefore missing for the corresponding daily variable derived. For each period of the diary to be considered incomplete, there must be no hot flashes of any severity recorded and the box indicating that there were no hot flashes must also not have been completed.

Continuous diary

- For the hot flash data, the diary will be considered incomplete if there are no hot flashes of any severity recorded and the box indicating that there were no hot flashes has also not been completed.
- For NTA not associated with hot flashes, the diary will always be considered complete

Skin Conductance

- If the skin conductance device has not recorded the hot flashes for a continuous period (e.g. due to battery failure) on a given day, then the whole day is considered incomplete and therefore missing for the corresponding daily variable derived.

For the calculation of the weekly scores, at least 4 complete days are needed for the derivations of the weekly values. The results from the complete days will then be averaged to give the weekly score.

Summary statistics will be based primarily on non-missing values. For hypothesis tests, estimates and confidence intervals (CIs) of the exploratory efficacy endpoints, missing values for efficacy endpoints will not be directly imputed. Missing values for endpoints analyzed via likelihood methods (e.g. mixed models) are handled within the analysis itself, under the assumption that the model specification is correct and that the data is missing at random. Sensitivity analyses may be conducted to check the robustness of the analysis results under alternative assumptions with regards to missing data.

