8.10.1.4 Night Time Awakenings

8.10.1.4.1 Night Time Awakenings Secondary to Hot Flashes

The number of NTA secondary to hot flashes will be the sum of the number of moderate and severe night time hot flashes recorded the following morning.

The NTA secondary to hot flashes will be summarized for each day and displayed graphically by day.

The average daily NTA secondary to hot flashes by week for each of Week -1, Week 1, and Week 2 will be equal to the average of the number of NTA secondary to hot flashes per day from Day -8 to Day -2 inclusive, from Day 1 to Day 7 inclusive, and from Day 8 to Day 14 inclusive, respectively. The weekly average number of NTA secondary to hot flashes per day and change from Week -1 will be summarized by treatment.

The same statistical analyses as described in Section 8.10.1.1 will be done for the weekly average change from Week -1 NTA secondary to hot flashes.

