8.10.1.4.2 Night Time Awakenings – Total

The total number of night time awakenings for Day Y will be equal to the number of NTA recorded the following morning.

The total NTA will be summarized for each day and displayed graphically by day.

The weekly average NTA per day for each of Week -1, Week 1, and Week 2 will be equal to the average of the number of NTA per day from Day -8 to Day -2 inclusive, from Day 1 to Day 7 inclusive, and from Day 8 to Day 14 inclusive, respectively. The weekly average number of NTA per day and change from Week -1 will be summarized by treatment.

The same statistical analyses as described in section 8.10.1.1 will be done for the weekly average change from Week -1 NTA.

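### Read literally, SAP 8.2 lets a blank daytime diary entry void a fully recorded night for awakenings secondary to hot flashes, an endpoint that uses only the night entry

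*SAP*

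**What the plan says.** SAP 8.2 opens its diary rules with a general statement about the daily scores of the efficacy section: "the daily derivation will not be calculated and will be treated as missing if the results of the corresponding day are incomplete". For the twice daily diary it then says that "if either period is not complete, then the whole day will be considered incomplete and therefore missing for the corresponding daily variable derived". A period counts as incomplete only if nothing at all was entered, that is, no flash was noted and the no-hot-flash box was left empty as well. For weekly scores, "at least 4 complete days are needed for the derivations of the weekly values". The same section says that missing efficacy values are not directly imputed.

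SAP 8.10.1.4.1 defines twice-daily-diary NTA secondary to hot flashes as "the sum of the number of moderate and severe night time hot flashes recorded the following morning". SAP 8.10.1.4.2 says that total NTA "will be equal to the number of NTA recorded the following morning". Neither definition uses the daytime entry. Both variables are averaged over the seven-day windows of Week -1, Week 1 and Week 2, and both are analysed with the mixed model of 8.10.1.1 on change from Week -1.

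Only NTA secondary to hot flashes is a listed exploratory endpoint (Protocol 8.3, SAP 3.5). For the continuous diary, SAP 8.2 has a separate line that treats awakenings without a hot flash as always complete. The twice daily diary has no such line.

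**The concern.** A 24-hour frequency or severity value needs both halves of the day, so for those variables it is sensible to drop the day when one half is blank. NTA secondary to hot flashes needs only the night half. Applying the whole-day test to it discards an observation that was made and recorded, because of a blank in a field the variable never uses.

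There are two consequences. Daily summaries and figures lose one valid night for each blank daytime entry. The 4-day minimum is also counted in whole days, so a woman with seven recorded nights can have no weekly value. If the lost week is Week -1, she has no change score and no baseline covariate, and she leaves the NTA model altogether. With 15 active subjects per dose, avoidable losses on this endpoint are worth preventing.

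**Working it through.** The documents state no missingness rate, number of lost weeks or power for NTA, so there is no planned figure to reproduce.

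**Inputs from the documents.** Seven days per week (SAP 8.10.1.4.1); both periods needed for a complete day, and at least 4 complete days per week (SAP 8.2); NTA secondary to hot flashes taken from the night entry only (SAP 8.10.1.4.1).

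**Inputs assumed.** Let d be the chance that a daytime entry is blank and n the chance that a night entry is blank, independent across periods and days. I take n = 10% and d = 10%, 20% and 30%.

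**Step 1, no assumptions needed.** Take a week with all seven nights recorded and k blank daytime entries. The literal rule leaves 7 − k complete days.

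| k | Complete days | Weekly NTA value, literal rule | Night-only rule |
|---|---|---|---|
| 0 | 7 | kept | kept on 7 nights |
| 1 | 6 | kept, 1 valid night lost | kept on 7 nights |
| 2 | 5 | kept, 2 valid nights lost | kept on 7 nights |
| 3 | 4 | kept, 3 valid nights lost | kept on 7 nights |
| 4 or more | 3 or fewer | missing | kept on 7 nights |

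**Step 2, expected valid nights discarded per week** = 7 × d × (1 − n):
- d = 10%: 7 × 0.10 × 0.90 = 0.63
- d = 20%: 7 × 0.20 × 0.90 = 1.26
- d = 30%: 7 × 0.30 × 0.90 = 1.89

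**Step 3, chance of losing a seven-day week** = P(X ≤ 3) with X ~ Binomial(7, q). Under the literal rule q = (1 − d)(1 − n); under a night-only rule q = 1 − n = 0.90.

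| d | q, literal rule | Week lost, literal rule | Week lost, night-only rule |
|---|---|---|---|
| 10% | 0.81 | 2.8% | 0.3% |
| 20% | 0.72 | 10.2% | 0.3% |
| 30% | 0.63 | 23.4% | 0.3% |

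With d = n = 5%, the chances are 0.25% and 0.02%.

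**Step 4, Week 2.** Subjects are in clinic for Days 1 to 7, are discharged on Day 8, and are readmitted from Day 14 to Day 15 (Protocol 8.4). Only Days 8 to 13 of Week 2 are completed wholly or partly at home. If Day 14 is complete, the week is lost when at most 2 of the other 6 days are complete, that is P(X ≤ 2) with X ~ Binomial(6, q):
- q = 0.81: 1.4%
- q = 0.72: 5.6%
- q = 0.63: 14.0%

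The night-only chance on the same basis is P(X ≤ 2) with X ~ Binomial(6, 0.90), or 0.1%.

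**The case against.** **The wording can be read more narrowly.** The sentence in SAP 8.2 is about hot flash data and ends by limiting the effect to the corresponding daily variable. A programmer might take this to mean the variable that needs the blank period. For NTA secondary to hot flashes the reading is strained: the variable is built from hot flash counts, the text voids the whole day, and the lead-in covers all daily efficacy scores. For total NTA the objection stands. That variable is a separate awakening count, and completeness in 8.2 is defined only through hot flash entries and the no-hot-flash box. A reader might infer that the plan discards valid nights for both NTA variables; the documents do not settle this for total NTA, which is also not a listed endpoint.

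**The rates are assumed and may be high.** This stands. A period is blank only if no flash of any severity is entered and the box is also left empty, and subjects enter with an average of at least 7 moderate to severe flashes a day. The two larger figures assume that daytime entries are blank two or three times as often as night entries, and nothing in the documents shows that. A reader might carry the seven-day figures over to Week 2 because most of it is at home; Step 4 shows that they are too high if Day 14 is completed in clinic.

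**The consequence is limited.** This also largely stands. A woman who loses Week 2 keeps her Week 1 value in the mixed model under missing at random, sensitivity analyses are allowed for, and the raw diary entries are listed. With one to three blank daytime entries and all nights recorded, the weekly value is still calculated. Week -1 is partly protected because eligibility needs at least 4 days of readings, although those are not defined as complete days.

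**A common complete-day basis has some value.** The whole-day rule makes all twice-daily-diary variables average over the same days. A night-only rule gives that up, which is a real but small cost.

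**Conclusion.** The point holds for NTA secondary to hot flashes. The literal rule discards recorded nights for a reason unrelated to the variable, and it can remove a weekly value from a woman with seven recorded nights. That much follows from the text without any assumed rate. For total NTA the plan is unclear and needs a stated rule.

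The size depends on unknown rates. With 10% blank nights and independent entries, week loss is uncommon at 10% blank daytime entries (2.8%, or about 1.4% for Week 2 with Day 14 complete) and material at around 20% or more (10.2%, or 5.6% for Week 2). Clustering of blanks within a subject would change these figures.

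A reader might infer that the rule undermines the efficacy analysis or biases it between arms. The documents give no support for either: 24-hour frequency and severity are handled sensibly, the NTA analyses are exploratory, and nothing indicates that blanks differ by treatment. The primary PK and safety objective is unaffected. This is a worthwhile improvement, not a serious fault.

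**What to change.** Add the following to the twice daily diary rules in SAP 8.2, before unblinding:

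- For 8.10.1.4.1, a day is complete when the night hot flash entry is complete, whatever the state of the daytime entry.
- For 8.10.1.4.2, a day is complete when that morning's awakening count is recorded. Defining it this way avoids carrying over the hot flash test, under which a recorded count beside blank hot flash fields could still be dropped.
- Weekly NTA values need at least 4 such nights.
- The whole-day rule continues to apply to the 24-hour frequency and severity variables.

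The cost is a few lines of text and a small programming change. No new data are collected. The one downside is that NTA and the 24-hour variables may be averaged over different days in the same week, which a table footnote can state.
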